### Project description for a human trial on colorectal cancer prophylaxis:

#### Aim:

Primary aim:

To investigate for a possible inhibitory effect from carrot juice on the recurrence of excised adenomas and, on the formation of metachronous adenomas in patients who are enrolled in a follow up program after resection of high risk colorectal adenomas.

An inhibitory effect of carrot juice will be measured by a combined endpoint of total number of recurrent adenomas multiplied with mean size of recurrent adenomas in the active arm or the placebo group. This difference will be significant if carrots mediate a 20% reduction in both size and numbers.

If the difference in number of polyps is 40 % or more, we will be able to prove this to be significant. If the difference in polyp size is larger than 40 % we will also achieve statistical difference between the 2 groups.

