#### Sample size:

Patients seen at the one-year follow up after high risk polyps have 40 % chance of having new polyp/polyps at the colonoscopy. The difference in polyp number found between treatment and control in rats was 40%. The difference in large polyps was 80 % but this is based upon small numbers. The possible effect in humans is unknown. A difference of 10 % or 20 % would be of clinical interest. To test for a difference of 20 % would demand the enrolment of 1248 persons, which is not realistic.

The study is dimensioned to prove a significant difference in number of polyps after 3 years and a significant difference in the combined endpoint (number x size) after 1 year of treatment. The expected effect in number of adenomas in the active and the control arm is a > 20% reduction (corresponding to a 50% relative reduction).

- 1. The recurrence rate is estimated to 40%
- 2. The acceptance rate to participate is 55%.
- 3. The exclusion rate is 20%
- 4. The total drop-out rate is expected to be 20%.
- 5. The drop-out patients are estimated to an average 6 months participation.

We assume 80% power and a standard deviation of 5%. Using a two-sided X2-test, a total of 726 patients have to be invited with a minimum of 328 patients to complete the trial. Due to the expected variability of the factors above, we aim to include a total of 400 patients equally to either case or controls. Achieving this number of included patients will require approximately 1.000 possible candidates to be invited. The combined capacity of the included centers is 1.600 eligible patients per year. Therefore, we estimate that the enrollment can be completed within 12 months.

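### The standard deviation of 5% in the sample size is undefined, has no place in the chi-square test named, and conflicts with the protocol's own 40% polyp rate, so number x size has no usable variance

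*Protocol*

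**What the plan says.** The Sample size section of the protocol gives one figure that it calls a measure of spread: "We assume 80% power and a standard deviation of 5" per cent. It does not say which outcome the figure belongs to, what the percentage is a percentage of, or where it comes from. The next sentence reads "Using a two-sided X2-test, a total of 726 patients have to be invited with a minimum of 328 patients to complete the trial".

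The other inputs in that section are a control rate (patients "have 40 % chance of having new polyp/polyps at the colonoscopy", repeated in the list as "The recurrence rate is estimated to 40" per cent) and an expected effect that "is a > 20% reduction (corresponding to a 50% relative reduction". I read these together as 40% against 20%. The section also names what the size is meant to deliver at one year: "a significant difference in the combined endpoint (number x size) after 1 year of treatment".

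The Aim section defines that endpoint as a "combined endpoint of total number of recurrent adenomas multiplied with mean size of recurrent adenomas", worded by arm. It asserts that the difference will reach significance if number and size each fall by 20%. No significance level is stated anywhere in the protocol.

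**The concern.** An SD belongs to a formula for comparing means. The test named compares proportions, and its variance follows from the two rates. So the 5% either serves no purpose, or describes something other than the test, or is the wrong label for another quantity.

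If it was meant for number x size, it conflicts with the protocol's own statement that about 60% of patients will have no polyp. A score with that many zeros cannot have so small a spread.

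At stake is the claim made for the one-year combined endpoint. Its power depends directly on a patient-level SD, and the protocol supplies none that can be used. Anyone who re-checks the size and carries the 5% forward would conclude that any relevant difference is certain to be detected.

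**Working it through.** **Inputs from the protocol.** Polyp rate 40%; effect read as 40% v 20%; power 80%; 400 randomised 1:1; dropout 20%, hence 400 x 0.8 = 320 completers, 160 per arm; 20% falls in both number and size, hence 0.8 x 0.8 = 0.64, a 36% reduction. **Assumed here:** two-sided alpha of 5%, because none is stated.

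**1. The printed 328.** The chi-square formula for 40% v 20% gives, per arm,
[1.96 x sqrt(2 x 0.3 x 0.7) + 0.84 x sqrt(0.24 + 0.16)]² / 0.20² = about 81.2, rounded up to 82, so 164 in total (182 with continuity correction). The printed 328 is exactly twice 164. The document does not show how it arose.

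A two-means formula with SD 5 does not give it either:
- 20-point difference: 2 x (1.96 + 0.84)² x 5² / 20² = 0.98, about 1 patient per arm.
- 8-point difference: 2 x (1.96 + 0.84)² x 5² / 8² = 6.1, so 7 per arm.
- SD 5 leads to 328 in total only for a difference of about 1.55 points, which the protocol never mentions.

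**2. SD of the yes/no outcome.** sqrt(0.4 x 0.6) = 0.490, or 49 points; at a 20% rate, sqrt(0.2 x 0.8) = 0.400, or 40 points.

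**3. SD of per-patient number x size.** For a non-negative score that is zero in a fraction 1 − p of patients, SD/mean is at least sqrt((1 − p)/p). Equality holds only if every patient with polyps has the same burden. With p = 0.4 this is sqrt(0.6/0.4) = 1.225, or 122%. The same bound applies to the polyp count. The Abstract gives the rate as about 30–40%; at 30% the two figures are sqrt(0.3 x 0.7) = 45.8 points and sqrt(0.7/0.3) = 153%, so the conclusion does not change.

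**4. Power for a 36% fall in mean number x size.** Set the control mean to 1 and let w be the CV of burden among patients with polyps. The control variance is (1 + w²)/0.4 − 1. The active variance is 0.64² x [(1 + w²)/p − 1], where p = 0.40 if all of the fall is in burden per patient with polyps, or p = 0.32 if the fall in number comes from fewer patients with polyps. Power = Φ(0.36 / sqrt((v0 + v1)/160) − 1.96).

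| w | Overall control SD/mean | Power, p = 0.40 | Power, p = 0.32 |
|---|---|---|---|
| 0 (minimum) | 122% | 88% | 84% |
| 0.5 (assumed) | 146% | 75% | 71% |
| 1.0 (assumed) | 200% | 48% | 45% |

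First cell as an example: v0 = 1.5, v1 = 0.4096 x 1.5 = 0.614; sqrt(2.114/160) = 0.115; 0.36/0.115 − 1.96 = 1.17; Φ = 0.88.

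If the minimum control SD of 122% applies in both arms: 0.36 / sqrt(3/160) − 1.96 = 0.67, power 75%. With 164 completers per arm instead of 160, each of these figures rises by about one point.

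**5. The yes/no comparison.** 40% v 20% with 160 per arm has about 98% power. The 5% does not enter.

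**The case against.** The strongest reply is that the 5% is a slip of wording and nothing printed depends on it. Two innocent readings exist. It may be the significance level, which is otherwise missing. Or it may be a standard error: sqrt((0.24 + 0.16)/160) = 0.050 is that of the difference in proportions at 160 per arm. The documents do not settle which. This part of the reply stands: a reader might infer that 328 is too small because the SD was too small, but 328 cannot have come from the 5%. It does not clear the sentence, however. A standard error is a result of the sample size and not an input to it, and a mislabelled alpha leaves number x size with no variability figure at all.

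Second, the Aim section words number x size by arm, and the analysis method may be in a statistical analysis plan that was not available. The per-patient comparison of means is therefore my assumption, as is the normal approximation for a skewed score. The wording by arm does not rescue the 5%, though. Total number times mean size over all adenomas in an arm is the sum of the patients' own number x size scores, so its uncertainty comes from the spread between patients. Its relative standard error at 160 patients is at least 122%/sqrt(160) = 9.7%.

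Third, the CVs of 0.5 and 1.0 are not in the protocol, and the best case of 84–88% exceeds the planned 80%. That is fair: the lower figures show sensitivity and are not estimates.

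A reader might also infer that 5% is impossible for every outcome in the trial, or that it is at least ten times too small. Neither is supported. The 40% rate puts no bound on the SD of polyp size among patients with polyps, or of compliance. For the yes/no outcome the ratio is 9.8 at 40% and 8 at 20%, and for number x size no ratio is meaningful while the unit of the 5% is unstated. Nor is it the plan's only variability input, since the rates supply the variance for the chi-square test; the gap concerns number x size.

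**Conclusion.** The point holds in this form: the stated SD of 5% has no outcome or unit, has no role in the chi-square test it accompanies, and is incompatible with the 40% rate for the yes/no outcome (49 points, or 40 at a 20% rate), the polyp count, and per-patient number x size (at least 122% of the mean). Every reading of it needs correction, and the 80% power has no valid basis for the one-year combined endpoint.

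The bounds in steps 2 and 3 follow from the protocol's own rate. The power figures also rest on two-sided 5% alpha, 160 completers per arm, a per-patient comparison of means and the 36% reduction. The 75% additionally needs equal SDs in both arms, and the ranges of 71–75% and 45–48% need assumed CVs. The documents therefore do not show that the trial is underpowered for number x size, and they do not show that 400 patients are enough. The 40% v 20% comparison is unaffected.

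**What to change.** In the Sample size section:

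- State what the 5% is. If it is the significance level, write *two-sided significance level 5%*; if it is something else, say so and state alpha separately.
- Remove the SD from the chi-square sentence and say that the variance follows from the assumed rates.
- For number x size, enter a justified per-patient SD that allows for patients without polyps (at least 122% of the control mean at a 40% rate), with a sensitivity range such as 146–200%.
- Restate the power, or the detectable reduction, for number x size at the existing 400 randomised and 320 completers.

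In the Aim section, align the assertion that 20% falls in both number and size will be significant with the restated figure.

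The cost is a few sentences and a short recalculation, with no change to procedures. The downside is a less favourable stated power for the combined endpoint. Whether 400 is adequate for that endpoint should be left to the recalculation and not asserted beforehand.

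### The stated minimum of 328 completers does not follow from its own inputs, which need 164 at an assumed two-sided 5% level; no significance level is given

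*Protocol*

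**What the plan says.** All the inputs are in the Sample size section of the protocol.

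- Control rate: "The recurrence rate is estimated to 40" per cent.
- Effect: the expected result "is a > 20% reduction (corresponding to a 50% relative reduction"), which makes the contrast 40% versus 20%.
- Power: "We assume 80% power and a standard deviation of 5" per cent. No significance level appears here or elsewhere in the protocol.
- Losses: "The acceptance rate to participate is 55" per cent; "The exclusion rate is 20" per cent; "The total drop-out rate is expected to be 20" per cent.
- Result: "Using a two-sided X2-test, a total of 726 patients have to be invited with a minimum of 328 patients to complete the trial".

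The section then sets enrolment at 400, split equally, and puts the invitations needed for this at about 1,000. Earlier it says: "To test for a difference of 20 % would demand the enrolment of 1248 persons".

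Under Outcome measures, the primary outcome is the number and size of polyps at one year. The count of patients with polyps in each arm is listed as secondary.

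**The concern.** A chi-square calculation for two proportions is fixed by the two rates, the power, the significance level and the allocation ratio. The protocol gives all of these except the significance level, and adds a standard deviation that the method does not use. If no ordinary significance level turns the stated inputs into 328, a reader cannot tell what error rate the trial was planned under or what effect it can detect.

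This is not detail that can wait for a statistical analysis plan. The protocol presents a finished calculation and calls its result a minimum. Because the calculation is for a proportion, its apparent precision may also be taken to cover the number and size primary outcome, which it does not size.

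**Working it through.** **Inputs.** p1 = 0.40, p2 = 0.20, power 80%, two-sided chi-square test, 1:1 allocation, all from Sample size. The significance level (alpha) is my assumption: 5%, with a range shown.

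**Completers needed.** With pooled variance, per arm,

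n = [z(1−α/2)·√(2p̄(1−p̄)) + z(0.80)·√(p1(1−p1) + p2(1−p2))]² / (p1−p2)², where p̄ = 0.30.

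At 5%: [1.960·√0.42 + 0.842·√0.40]² / 0.04 = 81.2, so 82 per arm and 164 in total. With continuity correction the result is 90.9, so 91 per arm and 182 in total. The protocol's 328 is not reproduced.

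| Two-sided alpha | Total | Total, continuity-corrected |
|---|---|---|
| 10% | 128 | 148 |
| 5% | 164 | 182 |
| 2.5% | 198 | 218 |
| 1% | 244 | 262 |
| 0.5% | 278 | 298 |

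For 328 to be the 80%-power total, alpha would have to be about 0.17% (0.26% with correction). At 5%, 164 per arm gives 97.9% power.

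**Possible origins of 328.** The text confirms none of these.

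- 328 = 2 × 164, so a total may have been read as a per-arm number.
- Alpha 1%, 90% power and continuity correction give 163.6, so 164 per arm and 328 in total, but this contradicts the stated 80% power.
- Alpha 1%, 80% power and continuity correction, divided by 0.8, give 130.99/0.8 = 163.7, so 164 per arm and 328 in total. That would be patients enrolled, whereas the protocol says completers.

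**From invitation to completion**, using the listed 55%, 20% and 20%:

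- Exclusion before invitation: 726 × 0.55 = 399 included; × 0.8 = 319 completers, 2.6% below 328.
- Exclusion after invitation: 726 × 0.55 × 0.8 = 319 included; × 0.8 = 256 completers, 22% below 328.
- Enrolment target: 400 × 0.8 = 320 completers.
- Invitations needed for 328 completers: 328/0.8 = 410 included; 410/0.55 ≈ 746 invited, or 410/0.55/0.8 ≈ 932.
- Invitations needed for 400 included: 400/0.55 = 727; before a 20% exclusion, 727/0.8 = 909.

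**What about 320 completers delivers** (160 per arm, proportion of patients with polyps only):

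| Contrast | Alpha 10% | Alpha 5% | Alpha 1% |
|---|---|---|---|
| 40% vs 20%, power | 99.0% | 97.7% | 91.3% |
| 40% vs 32%, power | 43.9% | 31.9% | 13.8% |
| Active-arm rate detectable at 80% power | 26.9% | 25.4% | 22.4% |

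**Two meanings of 20%.** A 20-point difference from 40% needs 164 at 5%, so the 1248 quoted for a 20% difference must mean something else, most plausibly a relative reduction, 40% versus 32%. The pooled formula for that gives 563.9 per arm and, with 10% loss, 563.9/0.9 = 626.6, so 627 per arm and 1254. The unpooled formula with 10% loss gives 561.2/0.9 = 623.5, so 624 per arm and 1248. Neither the formula nor the 10% is stated, so the sponsor must confirm the meaning.

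**The case against.** The best defence has three parts.

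First, the error is harmless in direction: 328 is more than 40% versus 20% requires, and the 400 to be enrolled give ample power for that contrast. This stands, and it limits the severity.

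Second, 726 may be right. Patient recruitment offers participation only where there is no contraindication, which suggests that exclusion comes before invitation. Then about 909 candidates, 727 invited, 400 included and 320 completers form one consistent sequence. It fits both 726 and the figure of about 1,000, and leaves 328 high by 8. This also stands. A reader might infer that 726 is the faulty figure, but the documents do not show that. What remains is that neither order quite reaches a stated minimum of 328, and that Sample size describes both 726 and about 1,000 as invited without saying where the 20% applies.

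Third, an undisclosed but legitimate calculation may lie behind 328. Several combinations return it, so it should not be dismissed unasked. But each departs from the stated power or from the description of 328 as completers, and the text confirms none. The listed assumption that drop-outs average six months of participation has no clear role, and no use of it was found that restores 328.

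**Conclusion.** Wrong as written, and should be fixed. 328 is twice the 164 completers that the stated inputs need at a two-sided 5% level, and it lies above the whole range of 128 to 298 for levels from 10% to 0.5%. The 164 rests on the assumed 5%. That 328 is not the 80%-power number holds at every level in that range, with or without continuity correction. The 5% standard deviation may be a mislabelled significance level, but only the sponsor can say.

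Two stronger conclusions are tempting and are not supported. One is that the trial is underpowered for 40% versus 20%; it is not. The other is that it could be cut to 164. That does not follow, because 164 concerns the proportion of patients with polyps at an optimistic effect, and does not size the primary outcome or the number-times-size endpoint for which the section says the study is dimensioned. For 40% versus 32%, about 320 completers give only about 32% power at 5%.

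The mismatch in patient flow is secondary: 319 or 256 completers from 726 invited, and 320 from 400 included, against 328.

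**What to change.** Wording only, in Sample size. Enrolment stays at 400, with no change to visits or data collection.

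1. Replace the 5% standard deviation with the two-sided significance level actually used, as confirmed by the sponsor.
2. Either disclose the calculation behind 328 (significance level, power, continuity correction, per arm or total), or stop calling it the minimum for 80% power. Do not adopt 164 as a target.
3. State what about 320 completers delivers. If the level is two-sided 5%, possible text is: *For the proportion of patients with polyps, about 320 completers give about 98% power for 40% versus 20%, 80% power for 40% versus about 25%, and about 32% power for 40% versus 32%. These figures concern a secondary outcome and do not size the number and size primary outcome.*
4. State whether the 20% exclusion comes before or after invitation, so that 726, about 1,000, 400 and the completer figure agree.
5. Label each 20% as absolute or relative, with the sponsor confirming whether 1248 refers to 40% versus 32%.

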#### Abstract:

**Background**: Carrot cultivars with a high content of falcarinol and falcarindiol have a strong antineoplastic effect in primed rats. The necessary corresponding blood concentration can easily be obtained in humans. High intake of carrots has been shown to reduce bowel cancer in humans in prospective cohort studies, and carotenes have been shown not to have any effect. A prophylactic effect against other cancers in humans especially of the lung and pancreas has also been indicated (1).

Patients who had polyps resected that are considered high risk will be offered a follow up (FU) colonoscopy after 1 year and after 3 years according to national guidelines. At this FU, about 30-40% of them will present with local recurrence or new polyps on colonoscopy.

The study will follow the new national guidelines with the approved acceptable timeframe adjustments, this meaning we will conduct the control colonoscopy at 3 months for piecemeal resection and a full colonoscopy at 1 year for all the patients involved in the study.

More than 90% of bowel cancers arise from adenomas and therefore prevention of adenomas is effective in preventing colorectal cancer.

**Method**: We aim to include and randomize 400 patients at the four institutions into two groups of equal size. It is expected that 80% of those will comply throughout one year of treatment. The patients are randomized blindly into one group receiving daily 100 ml active carrot juice and one group receiving 100 ml placebo. This amount has been calculated from our experiments in rats to be a sufficient volume as measured by serum concentration. After 1 year, we will register the number and sizes of polyps diagnosed in the 2 groups.

The primary aim is to investigate for a carrot-medicated inhibition of neoplastic transformation and growth in high risk humans.

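### The target of 400 patients, at the protocol's own 20% drop-out, gives 320 expected completers, 8 short of its stated minimum of 328; the effect on power is negligible

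*Protocol*

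**What the plan says.** The figures stand together in the Sample size section of the protocol. After a list of five planning factors, it concludes that "a total of 726 patients have to be invited with a minimum of 328 patients to complete the trial". The factors include a 55% acceptance rate, a 20% exclusion rate and a 20% total drop-out rate. For the patients who drop out, it adds: "The drop-out patients are estimated to an average 6 months participation".

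The enrolment target follows, with its reason: "Due to the expected variability of the factors above, we aim to include a total of 400 patients", split equally between the arms. About 1,000 candidates are to be invited to reach it. The Patient inclusion section keeps the same number, with the cohort rising to 400 by month 12. No section gives a higher target or a lower minimum.

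The Abstract has a related sentence about the 400: "It is expected that 80% of those will comply throughout one year of treatment".

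**The concern.** A minimum number of completers, a drop-out rate and an enrolment target are tied by one multiplication. Here the target times the completion rate falls below the minimum. The protocol also gives 400 as a rounding up that absorbs uncertainty, so a reader will assume a cushion above 328. There is none: the target is short before any factor turns out worse than expected.

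What is at stake is the credibility of a headline design figure. If recruitment and retention go exactly as expected, the trial ends below a number that its own protocol calls a minimum.

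**Working it through.** **Inputs, all from Sample size.** Minimum completers 328; target included 400 (200 per arm); total drop-out 20%; acceptance 55%; exclusion 20%; invited 726; recurrence in controls 40%; an expected reduction of 20 points (50% relative), so 40% v 20%; power 80%; two-sided chi-square test. Alpha is not stated; 5% is assumed below.

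**1. Can 328 be reproduced?** Pooled two-proportion formula, per arm:

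n = [z(0.975) x sqrt(2 x 0.30 x 0.70) + z(0.80) x sqrt(0.40 x 0.60 + 0.20 x 0.80)]^2 / 0.20^2

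= [1.960 x 0.648 + 0.842 x 0.632]^2 / 0.04 = 81.2, so 82 per arm and 164 in total (182 with continuity correction).

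The stated inputs do not give 328, which is exactly 2 x 164. With 90% power the total is 218 (238 with correction). The settings tried that come close use an effect the protocol does not state, such as 40% v 25% with continuity correction (330). The steps below take 328 as the protocol states it.

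**2. Expected completers from the target.** 400 x (1 - 0.20) = 320. Shortfall: 328 - 320 = 8, and 8/328 = 2.4%.

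**3. What 328 would need.** Included: 328/0.80 = 410. Largest drop-out compatible with 400 included: 1 - 328/400 = 18%. Multiplying in place of dividing gives 328 x 1.20 = 394, which would make 400 look sufficient. Whether this happened cannot be told from the protocol.

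**4. Is there a margin in 400?** 726 x 0.55 = 399 included, and 399 x 0.80 = 319 completers. So 400 is about what 726 invitations yield, with nothing added. If the 20% exclusion is applied as well, 726 x 0.80 x 0.55 = 319 included and 319 x 0.80 = about 256 completers. If each of 400 patients drops out independently with probability exactly 20%, the binomial chance of at least 328 completers is about 17%.

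**5. Effect on power (proportion with polyps, two-sided 5% alpha assumed).** Power = Phi{[0.20 x sqrt(n) - 1.270] / 0.632}, where 1.270 = 1.960 x 0.648.

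| Completers | Per arm | Power, 40% v 20% |
|---|---|---|
| 320 | 160 | 97.7% |
| 328 | 164 | 97.9% |

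With 160 per arm and 40% in controls, 80% power is reached at 25.4% in the active arm. That is a difference of 14.6 points, or 14.6/40 = 37% relative.

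**The case against.** **The gap is immaterial.** Eight patients change power by about 0.2 percentage points. This stands and sets the weight of the point. A reader might infer that the trial is underpowered because it misses its minimum; the calculation above does not support that.

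**328 is itself unsupported.** The stated inputs need about 164 completers, and against that number 320 is ample. This also stands. It does not remove the contradiction while the protocol calls 328 a minimum, but it means that the remedy must recalculate the requirement. Deleting 328 alone would leave 400 without a stated basis.

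**Drop-outs contribute six months on average.** Half credit gives 400 x (0.80 + 0.20 x 0.50) = 360 person-years, but the minimum counts patients who complete, so this does not close the gap.

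**Inviting 1,000 would yield more.** 1,000 x 0.80 x 0.55 = 440 included and 440 x 0.80 = 352 completers. The stated target is nevertheless 400.

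**The Abstract might seem to confirm 320 completers.** It does not. It speaks of complying with treatment. Under Design of the intervention, patients are followed whatever their compliance, so some who stop the juice may still have the one-year colonoscopy. The same section and Common pathway also provide for excluding non-compliant patients, so this does not rescue 328 either. The figure of 320 rests on the 20% drop-out in Sample size alone.

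**A reader might infer that the trial report would have to declare a failure to reach its required size.** Nothing in the protocol makes the analysis or its interpretation conditional on 328 completers.

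**Conclusion.** The sample-size statement is wrong as written: 400 included at 20% drop-out gives 320 expected completers, not the 328 called a minimum, and the suggested allowance for variability does not exist. This follows from the protocol's own three numbers and needs no outside assumption beyond reading total drop-out as not completing. It is a minor consistency error. The power figures rest on an assumed two-sided 5% alpha and concern the proportion of patients with polyps, which the protocol lists as a secondary outcome; they say nothing about power for the primary outcome of number and size of polyps.

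**What to change.** Reword Sample size without enrolling more patients:

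- State that 400 will be randomised and 320 are expected to complete, 160 per arm.
- Remove the suggestion that 400 gives a margin over 328.
- Replace the minimum of 328 with the completer requirement recalculated from the stated inputs, giving alpha, the two rates compared and the endpoint. For 40% v 20% with the stated test and power, and 5% alpha, that requirement is about 164 in total. Obtain any enrolment figure by dividing the requirement by 0.80.
- If a detectable difference for 160 per arm is quoted, name its endpoint and alpha. For the proportion with polyps (secondary outcome), at two-sided 5% alpha and 80% power, it is about 40% v 25.4%. It should not stand as the justification for the number-times-size endpoint, which needs its own.

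The cost is a few sentences and one recalculation. Recruitment, budget and conduct are unchanged.
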